5.3.2 Eliciting Adverse Event Information

A consistent methodology of non-directive questioning should be adopted for eliciting adverse event information at all patient evaluation timepoints. Examples of non-directive questions include the following:

"How have you felt since your last clinic visit?"

"Have you had any new or changed health problems since you were last here?"

5.3.3 Assessment of Severity of Adverse Events

The WHO toxicity grading scale (see Appendix 8) will be used for assessing adverse event severity (WHO 2003). Table 6 will be used for assessing severity for adverse events that are not specifically listed in the WHO toxicity grading scale.

Table 6 Adverse Event Severity Grading Scale for Events Not Specifically Listed in WHO Toxicity Grading Scale

Grade	Severity
1	Mild; transient or mild discomfort (<48 hours); no medical intervention or therapy required
2	Moderate; mild to moderate limitation in activity; some assistance may be needed; no or minimal medical intervention or therapy required
3	Severe; marked limitation in activity; some assistance usually required; medical intervention or therapy required; hospitalization possible
4	Life-threatening; extreme limitation in activity; significant assistance required; significant medical intervention or therapy required, hospitalization or hospice care probable

Notes: Developed by the Division of Microbiology and Infectious Diseases.

Regardless of severity, some events may also meet seriousness criteria. Refer to definition of a serious adverse event (see Section 5.2.2).

5.3.4 Assessment of Causality of Adverse Events

Investigators should use their knowledge of the patient, the circumstances surrounding the event, and an evaluation of any potential alternative causes to determine whether an

adverse event is considered to be related to the study drug, indicating "yes" or "no" accordingly. The following guidance should be taken into consideration:

- Temporal relationship of event onset to the initiation of study drug
- Course of the event, with special consideration of the effects of dose reduction, discontinuation of study drug, or reintroduction of study drug (as applicable)
- Known association of the event with the study drug or with similar treatments
- Known association of the event with the disease under study
- Presence of risk factors in the patient or use of concomitant medications known to increase the occurrence of the event
- Presence of non-treatment-related factors that are known to be associated with the occurrence of the event

For patients receiving combination therapy, causality will be assessed individually for each protocol-mandated therapy.

5.3.5 Procedures for Recording Adverse Events

Investigators should use correct medical terminology/concepts when recording adverse events on the Adverse Event eCRF. Avoid colloquialisms and abbreviations.

Only one adverse event term should be recorded in the event field on the Adverse Event eCRF.

5.3.5.1 Injection-Site Reactions

Local adverse events that occur within 24 hours after study drug administration and in the investigator's opinion are judged to be related to study drug injection should be captured as an "injection-site reaction" on the Adverse Event eCRF. An injection-related reaction that is localized should be marked as a "local injection-site reaction."

Associated signs and symptoms (e.g., injection-site erythema or injection-site rash) should be recorded on the dedicated Injection-Site Reaction eCRF. If a patient experiences both a local and systemic reaction to the same administration of study drug, each reaction should be recorded separately on the Adverse Event eCRF. Only for local injection-site reactions should the dedicated Injection-Site Reaction eCRF be used to capture the individual signs/symptoms.

5.3.5.2 Diagnosis versus Signs and Symptoms

For adverse events, other than injection-site reactions (see Section 5.3.5.1), a diagnosis (if known) should be recorded on the Adverse Event eCRF rather than individual signs and symptoms (e.g., record only liver failure or hepatitis rather than jaundice, asterixis, and elevated transaminases). However, if a constellation of signs and/or symptoms cannot be medically characterized as a single diagnosis or syndrome at the time of reporting, each individual event should be recorded on the Adverse Event eCRF. If a diagnosis is subsequently established, all previously reported adverse events based on signs and symptoms should be nullified and replaced by one adverse event report based

on the single diagnosis, with a starting date that corresponds to the starting date of the first symptom of the eventual diagnosis.

5.3.5.3 Adverse Events That Are Secondary to Other Events

In general, adverse events that are secondary to other events (e.g., cascade events or clinical sequelae) should be identified by their primary cause, with the exception of severe or serious secondary events. A medically significant secondary adverse event that is separated in time from the initiating event should be recorded as an independent event on the Adverse Event eCRF. For example:

- If vomiting results in mild dehydration with no additional treatment in a healthy adult, only vomiting should be reported on the eCRF.
- If vomiting results in severe dehydration, both events should be reported separately on the eCRF.
- If a severe gastrointestinal hemorrhage leads to renal failure, both events should be reported separately on the eCRF.
- If dizziness leads to a fall and consequent fracture, all three events should be reported separately on the eCRF.
- If neutropenia is accompanied by an infection, both events should be reported separately on the eCRF.

All adverse events should be recorded separately on the Adverse Event eCRF if it is unclear as to whether the events are associated.

5.3.5.4 Persistent or Recurrent Adverse Events

A persistent adverse event is one that extends continuously, without resolution, between patient evaluation timepoints. Such events should only be recorded once on the Adverse Event eCRF. The initial severity (intensity or grade) of the event will be recorded at the time the event is first reported. If a persistent adverse event becomes more severe, the most extreme severity should also be recorded on the Adverse Event eCRF. If the event becomes serious, it should be reported to the Sponsor immediately (i.e., no more than 24 hours after learning that the event became serious; see Section 5.4.2 for reporting instructions). The Adverse Event eCRF should be updated by changing the event from "non-serious" to "serious," providing the date that the event became serious, and completing all data fields related to serious adverse events.

A recurrent adverse event is one that resolves between patient evaluation timepoints and subsequently recurs. Each recurrence of an adverse event should be recorded as a separate event on the Adverse Event eCRF.

5.3.5.5 Abnormal Laboratory Values

Not every laboratory abnormality qualifies as an adverse event. A laboratory test result must be reported as an adverse event if it meets any of the following criteria:

- Is accompanied by clinical symptoms

- Results in a change in study treatment (e.g., dosage modification, treatment interruption, or treatment discontinuation)
- Results in a medical intervention (e.g., potassium supplementation for hypokalemia) or a change in concomitant therapy
- Is clinically significant in the investigator's judgment

It is the investigator's responsibility to review all laboratory findings. Medical and scientific judgment should be exercised in deciding whether an isolated laboratory abnormality should be classified as an adverse event.

If a clinically significant laboratory abnormality is a sign of a disease or syndrome (e.g., alkaline phosphatase and bilirubin 5 \times ULN associated with cholestasis), only the diagnosis (i.e., cholestasis) should be recorded on the Adverse Event eCRF.

If a clinically significant laboratory abnormality is not a sign of a disease or syndrome, the abnormality itself should be recorded on the Adverse Event eCRF, along with a descriptor indicating whether the test result is above or below the normal range (e.g., "elevated potassium," as opposed to "abnormal potassium"). If the laboratory abnormality can be characterized by a precise clinical term per standard definitions, the clinical term should be recorded as the adverse event. For example, an elevated serum potassium level of 7.0 mEq/L should be recorded as "hyperkalemia."

Observations of the same clinically significant laboratory abnormality from visit to visit should only be recorded once on the Adverse Event eCRF (see Section [5.3.5.4](#) for details on recording persistent adverse events).

5.3.5.6 Abnormal Vital Sign Values

Not every vital sign abnormality qualifies as an adverse event. A vital sign result must be reported as an adverse event if it meets any of the following criteria:

- Is accompanied by clinical symptoms
- Results in a change in study treatment (e.g., dosage modification, treatment interruption, or treatment discontinuation)
- Results in a medical intervention or a change in concomitant therapy
- Is clinically significant in the investigator's judgment

It is the investigator's responsibility to review all vital sign findings. Medical and scientific judgment should be exercised in deciding whether an isolated vital sign abnormality should be classified as an adverse event.

If a clinically significant vital sign abnormality is a sign of a disease or syndrome (e.g., high blood pressure), only the diagnosis (i.e., hypertension) should be recorded on the Adverse Event eCRF.

Observations of the same clinically significant vital sign abnormality from visit to visit should only be recorded once on the Adverse Event eCRF (see Section [5.3.5.4](#) for details on recording persistent adverse events).

5.3.5.7 Abnormal Liver Function Tests

The finding of an elevated ALT or AST ($>3 \times$ baseline value) in combination with either an elevated total bilirubin ($\geq 2 \times$ ULN) or clinical jaundice in the absence of cholestasis or other causes of hyperbilirubinemia is considered to be an indicator of severe liver injury (as defined by Hy's law). Therefore, investigators must report as an adverse event of special interest the occurrence of either of the following:

- Treatment-emergent ALT or AST $>3 \times$ baseline value in combination with total bilirubin $>2 \times$ ULN (of which $\geq 35\%$ is direct bilirubin)
- Treatment-emergent ALT or AST $>3 \times$ baseline value in combination with clinical jaundice in the absence of cholestasis or other causes of hyperbilirubinemia

The most appropriate diagnosis or (if a diagnosis cannot be established) the abnormal laboratory values should be recorded on the Adverse Event eCRF (see Section [5.3.5.2](#)) and reported to the Sponsor immediately (i.e., no more than 24 hours after learning of the event), either as a serious adverse event or an adverse event of special interest (see Section [5.4.2](#)).

5.3.5.8 Deaths

All deaths that occur during the protocol-specified adverse event reporting period (see Section [5.3.1](#)), regardless of relationship to study drug, must be recorded on the Adverse Event eCRF and immediately reported to the Sponsor (see Section [5.4.2](#)). This includes death attributed to progression of hemophilia.

Death should be considered an outcome and not a distinct event. The event or condition that caused or contributed to the fatal outcome should be recorded as the single medical concept on the Adverse Event eCRF. Generally, only one such event should be reported. If the cause of death is unknown and cannot be ascertained at the time of reporting, "unexplained death" should be recorded on the Adverse Event eCRF. If the cause of death later becomes available (e.g., after autopsy), "unexplained death" should be replaced by the established cause of death. The term "sudden death" should not be used unless combined with the presumed cause of death (e.g., "sudden cardiac death").

If the death is attributed to progression of hemophilia, "hemophilia progression" should be recorded on the Adverse Event eCRF.

Deaths that occur after the adverse event reporting period should be reported as described in Section [5.6](#).

5.3.5.9 Preexisting Medical Conditions

A preexisting medical condition is one that is present at the screening visit for this study. Such conditions should be recorded on the General Medical History and Baseline Conditions eCRF.

A preexisting medical condition should be recorded as an adverse event only if the frequency, severity, or character of the condition worsens during the study. When recording such events on the Adverse Event eCRF, it is important to convey the concept that the preexisting condition has changed by including applicable descriptors (e.g., "more frequent headaches").

5.3.5.10 Lack of Efficacy or Worsening of Hemophilic Bleeds

At any time during the study an unexpected worsening of hemophilia-related bleeding, as judged by the investigator, should be recorded as an adverse event. For example, increased severity (e.g., increased number of FVIII doses required to stop bleeds compared with before study entry) or frequency of bleeds. Hemophilia worsening should be documented as an adverse event on the Adverse Event eCRF, conveying that the underlying condition has changed by including applicable descriptors (e.g., "increased clinical severity of hemophilia"). A clinically significant bleed (i.e., intracranial, retroperitoneal) does not by itself constitute loss of efficacy, unless it is associated with features indicating worsening of the underlying hemophilia phenotype. Events that are clearly consistent with the expected pattern of the underlying disease and do not indicate an unexpected worsening in severity or frequency should not be recorded as adverse events. These data will be reflected in efficacy assessment data only.

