5.2.1 Adverse Events

According to the ICH guideline for Good Clinical Practice, an adverse event is any untoward medical occurrence in a clinical investigation subject administered a pharmaceutical product, regardless of causal attribution. Therefore, an adverse event can be any of the following:

- Any unfavorable and unintended sign (including an abnormal laboratory finding), symptom, or disease temporally associated with the use of a medicinal product, whether or not considered related to the medicinal product

- Any new disease or exacerbation of an existing disease (a worsening in the character, frequency, or severity of a known condition), except as described in Section 5.3.5.10
- Recurrence of an intermittent medical condition (e.g., headache) not present at baseline
- Any deterioration in a laboratory value or other clinical test (e.g., ECG, X-ray) that is associated with symptoms or leads to a change in study treatment or concomitant treatment or discontinuation from study drug
- Adverse events that are related to a protocol-mandated intervention, including those that occur prior to assignment of study treatment (e.g., screening invasive procedures such as biopsies)

Bleeds considered as serious adverse events should be reported as serious adverse events on the eCRF. New nonserious bleeds, consistent with patients' pre-study disease, will not be considered adverse events and will not be recorded on the eCRF (but should be captured on the bleed/medication questionnaire).

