5.3.5.11 Hospitalization or Prolonged Hospitalization

Any adverse event that results in hospitalization (i.e., in-patient admission to a hospital) or prolonged hospitalization should be documented and reported as a serious adverse event (per the definition of serious adverse event in Section 5.2.2), except as outlined below.

An event that leads to hospitalization under the following circumstances should not be reported as an adverse event or a serious adverse event:

- Hospitalization for respite care
- Planned hospitalization required by the protocol (e.g., for study drug administration or insertion of access device for drug administration)
- Hospitalization for a preexisting condition, provided that all of the following criteria are met:

The hospitalization was planned prior to the study or was scheduled during the study when elective surgery became necessary because of the expected normal progression of the disease

The patient has not experienced an adverse event

An event that leads to hospitalization under the following circumstances is not considered to be a serious adverse event, but should be reported as an adverse event instead:

- Hospitalization that was necessary because of patient requirement for outpatient care outside of normal outpatient clinic operating hours

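### Protocol 5.3.5.10 does not limit its adverse event exclusion to nonserious events, so a non-fatal serious bleed typical for the patient can be recorded as an SAE or left out

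*Protocol*

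**What the plan says.** Protocol 5.3.5.10 covers lack of efficacy and worsening of bleeding. Unexpected worsening, as the investigator judges it, is an adverse event. Events that plainly fit the usual course of the disease and "do not indicate an unexpected worsening in severity or frequency should not be recorded as adverse events" are treated differently: "These data will be reflected in efficacy assessment data only". The exclusion carries no limit by seriousness.

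Protocol 5.2.1 gives a rule for serious bleeds: "Bleeds considered as serious adverse events should be reported as serious adverse events on the eCRF". Its next sentence says that new nonserious bleeds in keeping with pre-study disease "will not be considered adverse events and will not be recorded on the eCRF", although they go into the bleed questionnaire. Earlier in 5.2.1, one of the five bullets defining an adverse event (new disease or exacerbation of an existing one) ends with the words "except as described in Section 5.3.5.10".

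Three further rules bear on the point.

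- Section 5.2.2 defines an SAE as an adverse event that meets a seriousness criterion.
- Under 5.3.5.11, an adverse event that leads to admission "or prolonged hospitalization should be documented and reported as a serious adverse event".
- Section 5.3.5.8 requires every death in the reporting period to be recorded: "This includes death attributed to progression of hemophilia".

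Adverse events are summarized by arm to compare emicizumab with no prophylaxis (Protocol 6.5), and SAP 4.7.2 adds a separate SAE summary.

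**The concern.** For one kind of event the two sections give opposite instructions. A site that turns first to 5.3.5.10, the section devoted to hemophilic bleeding, could conclude that a bleed typical for the patient is not an adverse event. It would then never reach the seriousness test in 5.2.2 or the hospitalization rule in 5.3.5.11, because both start from something that is already an adverse event. A site that starts from the serious-bleed sentence in 5.2.1 would report the same bleed as an SAE.

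Two things are at stake. The 24-hour reporting duty in 5.4 attaches to SAEs, so a bleed that is never recorded as one can miss it. The SAE summaries by arm would also depend partly on which section each site followed.

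The extension phase is the weakest spot. Section 5.3.5.10 relies on the efficacy data to hold the excluded events. Sections 4.5.7 and 4.5.8.2 stop bleed and medication collection once the extension starts, and the concomitant-medication footnote in Appendix 1-B says bleed treatments are not collected there either. In that phase an excluded bleed would have no bleed questionnaire record.

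**Working it through.** The question is mainly one of reading the sections together, so I set the possible cases side by side.

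| Type of bleed | Following 5.2.1 | Following 5.3.5.10 | Agree? |
|---|---|---|---|
| Nonserious, fits the expected pattern | Not an adverse event | Not an adverse event | Yes |
| Unexpected worsening | Adverse event; SAE if serious | Adverse event | Yes |
| Fatal | Recorded (5.3.5.8) | Recorded (5.3.5.8) | Yes |
| Serious, non-fatal, fits the expected pattern | SAE | Not recorded as an adverse event | **No** |

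Only the last row conflicts. The next question is whether another rule settles it.

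- *Stated precedence:* none. The one cross-reference runs from 5.2.1 to 5.3.5.10 and covers only the exacerbation bullet.
- *Seriousness and hospitalization rules (5.2.2, 5.3.5.11):* both presuppose an adverse event, so they do not restore an event already excluded.
- *Preexisting conditions (5.3.5.9):* recorded as adverse events only if they worsen. This leans toward the 5.3.5.10 reading.
- *Adverse event footnotes in Appendices 1-A and 1-B:* both repeat the unexpected-worsening trigger and neither repeats the serious-bleed rule.

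The documents give no share of bleeds that are serious, so there is no plan figure to reproduce. For scale only, take the planning inputs in Protocol 6.1: ABR 4 on emicizumab and 18 on control; 28, 28 and 14 patients; 0.5 units of time.

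Expected bleeds = n × ABR × 0.5:
- Arm A and Arm B: 28 × 4 × 0.5 = 56 each
- Arm C: 14 × 18 × 0.5 = 126

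Expected serious bleeds = expected bleeds × s, where the serious share s is an assumption:

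| s | Arm A or B (each) | Arm C |
|---|---|---|
| 0.5% | 0.28 | 0.63 |
| 1% | 0.56 | 1.26 |
| 2% | 1.12 | 2.52 |
| 5% | 2.80 | 6.30 |

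Counting 24 weeks as 0.46 year instead lowers Arm C to 14 × 18 × 0.46 = 116 bleeds and each emicizumab arm to 28 × 4 × 0.46 = 52, which changes nothing of substance.

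For a given s, the table is a ceiling on the expected number of events in question. Only those that are non-fatal, fit the expected pattern and occur at a site following 5.3.5.10 would be lost. If s were equal in all arms, such events would be 18 / 4 = 4.5 times as frequent per patient in the control arm. One affected patient is 1/14 = 7.1% of Arm C and 1/28 = 3.6% of Arm A or B.

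**The case against.** The best defense is that 5.2.1 already answers the question. Its serious-bleed sentence stands alone and orders reporting directly, and the sentence after it limits the exemption to nonserious bleeds. The cross-reference qualifies one bullet of five; the first bullet, on any unfavorable and unintended sign, symptom or disease, is untouched. Section 5.3.5.10 can be read as dealing with change in the bleeding pattern and leaving serious bleeds to 5.2.1. Much of this stands, and it is probably what the sponsor intended. It does not close the gap: 5.3.5.10 is worded without limit, nothing says which section governs, and the 5.2.1 sentence speaks of bleeds considered SAEs, a status that 5.2.2 makes conditional on being an adverse event.

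Other parts of the defense narrow the point and should be accepted.

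- A reader might infer that 5.3.5.10 takes intracranial or retroperitoneal bleeds off the safety record, because it mentions them just before the exclusion. That sentence says only: "A clinically significant bleed (i.e., intracranial, retroperitoneal) does not by itself constitute loss of efficacy". It concerns loss of efficacy, not recording. Many life-threatening bleeds would also fail the exclusion's own conditions, since they would not clearly fit the usual pattern or would show unexpected severity.
- A reader might see a second contradiction with 5.3.5.8. That section requires all deaths to be recorded, so it recovers fatal cases.
- Hospitalized bleeds are not wholly invisible in the randomized period. The questionnaire captures bleeds, and days hospitalized are summarized by arm (Protocol 6.7, SAP 4.5.3).
- New wording cannot act backward. Footnotes in Appendices 2-A to 2-C say sampling for Arms A to C stopped in March 2021, which suggests that the randomized control period is already over.

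**Conclusion.** The inconsistency is real and narrow: a serious, non-fatal bleed that is typical for the patient is an SAE under 5.2.1 and is left out under 5.3.5.10 as written. The primary endpoint is unaffected, because bleeds reach it through the questionnaire. The safety comparison is descriptive, so no test or alpha level is involved. The number of affected events cannot be derived from the documents. The illustration rests on the planning bleed rates and an assumed serious share of 0.5% to 5%, and suggests small counts in every arm.

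A reader might go further and infer that the SAE table is biased by arm, with investigators in this open-label study calling control bleeds expected and emicizumab bleeds unexpected. That is possible, but nothing in the documents shows it. The 4.5-fold ratio holds only at the planning rates with the same serious share in each arm. It describes how often the question could arise, not how sites answered it.

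The practical weight lies in 24-hour reporting and in the extension phase, where the questionnaire backstop is gone. The passages should be reconciled.

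**What to change.** In Protocol 5.3.5.10, limit the exclusion to nonserious events and cross-refer to the 5.2.1 rule: a bleed that meets a seriousness criterion is reported as an SAE in every arm, and in the extension phase, whether or not it was expected. This restates what 5.2.1 already says and changes no endpoint or treatment.

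For the randomized period, before SAEs are summarized by arm, check the hospitalization data on the eCRF and the bleed questionnaire records against the SAE record. Resolve with the site any bleed that led to admission but has no matching SAE.

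The cost is one sentence, a site notification, one data reconciliation check and possibly a few more reported SAEs.
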